6. INVESTIGATIONAL PLAN

6.1. Overall Study Design

This open-label Phase 2 study will evaluate the efficacy, safety, PK, and PD of PT2385 in patients with VHL disease who have at least 1 measurable VHL disease-associated ccRCC tumor (as defined by RECIST 1.1). PT2385 will be administered orally at a dosage of 800 mg twice daily. Treatment will be continuous; the drug will be administered twice daily every day. Patients will be entered in the study after meeting all inclusion criteria and no exclusion criteria. This study will be conducted with a 2-stage design, which allows for an early assessment of futility. A response will be defined as either a PR or CR occurring at any time after initiation of treatment, based on assessment of ccRCC tumors. All responses must be confirmed after the initial response is documented. Changes in VHL disease-associated non-ccRCC tumors will also be evaluated independently by modifying RECIST 1.1 criteria to assess tumors in individual organ systems independently rather than collectively.

Twenty-five patients will be enrolled during the first stage. A Data Monitoring Committee (DMC) will perform the safety review for the first 6 patients and the futility analysis for Stage 1 of the study. The DMC will review safety and any treatment-limiting toxicities to confirm whether the study should continue to enroll or if modifications to the protocol are needed. The DMC will review the response data from the first 25 patients to determine if at least 3 patients have a confirmed PR or better in ccRCC tumors and that the threshold for opening Stage 2 has been met. Treatment-limiting toxicities will be assessed according to Section 6.4. Study termination criteria are presented in Section 6.5.

In the second stage of the study, 25 additional patients will be enrolled, to a maximum accrual of 50 patients.

Patients will undergo clinical and laboratory evaluations every 2 weeks for the first 4 weeks and then every 4 weeks (i.e., 28 days) according to the Schedule of Events. Patients will be evaluated radiologically for evidence of response or progression approximately 12 weeks after initiation of treatment and every 12 weeks thereafter while continuing in the study. Patients with evidence of stable disease or disease response, i.e., CR or PR, will continue to receive treatment in the absence of serious toxicity. Patients who demonstrate disease progression of their ccRCC tumors at any time will be withdrawn from study treatment.

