Patients who need surgical intervention for VHL-disease associated non-ccRCC tumors, and who do not meet the RECIST 1.1 criteria for progression of the ccRCC tumors, while participating in the study, may be allowed to resume study drug administration, as long as study drug has been withheld no more than 8 weeks, and there is no progression of ccRCC tumors. Patients with non-ccRCC tumors that meet the RECIST 1.1 criteria for progression will be withdrawn from study treatment.

Patients who undergo resection of non-renal VHL disease-associated lesions, and who do not meet the RECIST 1.1 criteria for progression of those lesions, may resume treatment with PT2385 once the surgical incisions have adequately healed, and if in the opinion of the Principal Investigator, the patient is likely to experience clinical benefit.

Patients who discontinue from study treatment for any reason will be followed every 6 months either by telephone or office visit to determine their medical history, surgical history,

disease status, and survival status. These patients will be followed for up to 3 years following the completion of enrollment in the study or until the patient either withdraws consent or dies.

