6.4. Dose Adjustment Criteria

For patients who experience a treatment-limiting toxicity and require dose modification, the guidelines in Table 1 will be used to determine the dose modification required. If the Investigator believes that the guidelines should not apply, he/she will contact the Sponsor's medical monitor to discuss the circumstances and the appropriate dose modification.

Patients requiring surgical intervention for non-renal lesions during the course of the study should have study drug treatment interrupted. Study drug may be restarted when the surgical incision has adequately healed, provided there is no evidence of progression of ccRCC, and study drug interruption has been for no more than 8 weeks. Patients with non-renal lesions that meet the RECIST 1.1 criteria for progression will be withdrawn from study treatment.

Patients requiring study drug interruption for more than 3 weeks will be withdrawn from study treatment, except in the instance of interruption for surgery as noted above.

Treatment-limiting toxicity in the first 6 patients will be defined as any of the following events occurring in the first 28 days of treatment, graded using the National Cancer Institute Common Terminology Criteria for Adverse Events Version 4.03 (NCI CTCAE 4.03):

- Hematologic
 - Febrile neutropenia (absolute neutrophil count < 1,000/ μ L plus body temperature \geq 38.5°C)
 - Grade 4 neutropenia lasting for > 5 days (in the absence of growth factor support)
 - Grade 3 thrombocytopenia with bleeding
 - Grade 4 thrombocytopenia
 - Grade 4 anemia unexplained by underlying disease
- Gastrointestinal
 - Grade 3 or 4 nausea, vomiting, or diarrhea that persists for > 48 hours despite optimal antiemetic or antidiarrheal treatment

- Hepatic
 - Grade 3 or greater increase in transaminase levels, if confirmed upon repeat testing within 48 hours
 - Grade 3 or 4 increase in transaminase levels if accompanied by a Grade 2 increase in bilirubin level and an alkaline phosphatase level > 2 × upper limit of normal (ULN)
- Other
 - Any other study drug-related Grade 3 or 4 non-hematologic toxicity, except for Grade 3 asymptomatic hypoxia unless considered clinically significant by the Investigator
 - Any study drug-related Grade 3 or 4 laboratory toxicity that does not resolve within 48 hours and is considered clinically significant by the Investigator.

Table 1Guidelines for Dose Modification

Toxicity	Occurrence	Action

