8.2. Concomitant Medications

Patients may not receive chemotherapy, anti-neoplastic hormonal therapy, or any investigational anti-neoplastic agent during the course of this study. Immunosuppressive agents are prohibited during the course of study participation. Systemic steroids may not be used in the study at doses greater than the equivalent of 20 mg prednisone daily with the exception of intermittent use for the treatment of emesis.

Patients may receive limited fraction palliative radiotherapy after 12 weeks to control local tumor-related symptoms if irradiation is unlikely to induce major organ toxicity and only if in the opinion of the Investigator, the patient does not have progressive disease. The radiation field cannot encompass a target lesion. Radiation to a target lesion is considered progressive disease and the patient should be removed from study treatment.

Antiemetic agents may be used for the treatment of nausea and vomiting but may not be administered prophylactically. Granulocyte colony-stimulating factor (G-CSF) should be administered only for severe or prolonged neutropenia or for neutropenic sepsis. There will be no constraint on the use of growth factors during subsequent treatment; however, prophylactic use is discouraged and adherence to the American Society of Clinical Oncology (ASCO) guidelines is recommended. Erythropoietin should not be administered during the first 28 days of study drug treatment.

Patients should receive all necessary supportive care, including blood products, transfusions, antibiotics, pain medications, bisphosphonates, and replacement hormonal therapies (insulin, thyroid hormones, estrogen/progesterone) as needed, but levels should be closely monitored.

PT2385 is primarily metabolized by UGT2B17, UGT2B7, UGT2B15, CYP2C19 and CYP3A4. Strong inhibitors of CYP2C19 and CYP3A4 should be avoided in patients receiving PT2385 (Appendix 6).

PT2385 has been shown to induce the enzymes CYP3A4 and CYP2B6 in cultured human hepatocytes. Simcyp PBPK model simulations indicate weak-to-moderate CYP3A4 substrate midazolam DDIs (~50% reduction in midazolam AUC) at the clinically relevant PT2385 doses. Simulations also indicate that PT2385 is a weak CYP2B6 inducer (< 11%

Peloton Therapeutics, Inc. CONFIDENTIAL

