10. ASSESSMENT OF EFFICACY

10.1. Efficacy Parameters

Primary endpoint: Best confirmed response in VHL disease-associated ccRCC tumors, defined as the proportion of the best confirmed response of CR or PR (as assessed by the Independent Review Committee (IRC)) as determined by RECIST 1.1, modified to follow ccRCC tumors only. ORR is defined as the proportion of patients with a best confirmed response of CR or PR.

Secondary endpoints:

- Progression-free survival (PFS) in VHL disease-associated ccRCC tumors, defined as the interval from the start of study treatment until the earlier of the first documentation of disease progression determined by RECIST 1.1 or death from any cause, and calculated for patients with a best confirmed response of CR or PR
- Duration of response (DOR) in VHL disease-associated ccRCC tumors, defined as the interval from the first documentation of response, as determined by RECIST 1.1, to the earlier of the first documentation of disease progression or death from any cause, and calculated for the patients with a best confirmed response of CR or PR
- Time to response (TTR) in VHL disease-associated ccRCC tumors, defined as the interval from the start of study treatment to the first documentation of a response, as determined by RECIST 1.1, and calculated for patients with a best confirmed response of CR or PR
- Best confirmed response, PFS, DOR, and TTR for non-ccRCC tumors associated with VHL disease in different organ systems, by modifying RECIST 1.1 criteria to assess tumors in individual organ systems (Appendix 4)

Exploratory endpoint:

• Changes in PD markers (e.g., serum EPO)

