13.3.4. Efficacy Analyses

The primary summaries of all response data will be based on the Efficacy Analysis Set.

Response of ccRCC tumors will be measured by contrast enhanced computerized tomography (CT) or magnetic resonance image (MRI) scan and assessed according to RECIST 1.1, modified to follow ccRCC tumors only.

Response assessments of ccRCC CR and PR should be confirmed by a second assessment. Where confirmed responses are required, the date of the first assessment will be used in all analyses. In the case that the confirmation assessment is not available, the assessment at the next scheduled time point will be used for confirmation. If there are no assessments, the response will be taken to be unconfirmed and a non response.

The ccRCC ORR is defined as the proportion of patients for whom the best confirmed ccRCC response is CR or PR, determined by RECIST 1.1. Estimates of the ccRCC ORR along with the associated 90% and 95% exact binomial confidence intervals (Clopper Pearson) will be provided. The binomial probability that the observed ccRCC ORR is > 0.15 will be calculated. Best confirmed ccRCC response will be summarized.

The ccRCC PFS is defined the interval from the start of study treatment until the earlier of the first documentation of ccRCC disease progression determined by RECIST 1.1 or death from any cause, whichever occurs first. Renal cell carcinoma PFS will be right censored for patients who meet one of the following conditions: 1) no post baseline disease assessments, 2) non protocol systemic anticancer treatment started before documentation of disease progression or death, 3) surgery that is considered to affect response before documentation of disease assessment visit, 5) alive and does not have documentation of disease progression before a data analysis cutoff date. The Kaplan-Meier (KM) method will be used to estimate the distribution of ccRCC PFS. Quartiles including the median will be estimated by KM method along with their 95% confidence intervals. A figure showing the estimated ccRCC PFS distribution will be provided. KM cumulative estimators along with the associated 95% CIs will be provided for ccRCC PFS rates at 26, 39 and 52 weeks. Duration of follow up for ccRCC PFS will be summarized according to the KM estimate of potential follow up also termed "reverse Kaplan-Meier."

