The ccRCC DOR will be calculated for patients who achieve a ccRCC CR or PR. For such patients, the ccRCC DOR is defined as the interval from first documentation of response, as determined by RECIST 1.1, to the earlier of the first documentation of disease progression or death from any cause. Dates of progression and censoring will be determined as described for the analysis of ccRCC PFS. Kaplan-Meier methods will be used to estimate the distribution of ccRCC DOR. Quartiles including the median will be estimated by KM method along with their 95% confidence intervals. KM cumulative estimators along with the associated 95% CIs will be provided for ccRCC DOR rates at 26, 39 and 52 weeks. These estimates will be used as estimates of durable response.

The ccRCC TTR will be calculated for patients who achieve a ccRCC CR or PR. Renal cell carcinoma TTR is defined as the interval from the start of study treatment to the first documentation of a ccRCC response of PR or better, as determined by RECIST 1.1.

The maximum percent decrease in ccRCC total tumor burden will be displayed using waterfall plots.

Summaries of the response endpoints will also be provided for subgroups of the Efficacy Analysis Set as follows: Subgroups will be defined according to blood level of PT2385 based on the PK assessments and duration of PT2385 treatment. The analyses of ccRCC ORR, ccRCC PFS, ccRCC best confirmed response, ccRCC DOR, and ccRCC TTR will be performed in each of these subgroups.

The ORR, PFS, best confirmed response, DOR, and TTR will be summarized for the nonccRCC tumors associated with VHL disease based on the subgroups of patients in the Efficacy Analysis Set who have the particular type of tumor. The determination of best response and date of progression will be determined by modifying RECIST 1.1 criteria to assess tumors in individual organ systems independently (e.g., VHL disease-associated solid tumors in the pancreas or adrenal gland, or hemangioblastomas or retinal angiomas).

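### Organ-level response for non-ccRCC tumors has no cut-off at permitted surgery, so a resected lesion could be scored as a response to PT2385

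*Combined protocol and SAP*

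**What the plan says.** **Endpoint.** Section 10.1 lists as secondary: "Best confirmed response, PFS, DOR, and TTR for non-ccRCC tumors associated with VHL disease in different organ systems". Section 13.3.4 summarizes these, together with ORR, "based on the subgroups of patients in the Efficacy Analysis Set who have the particular type of tumor", and adds: "The determination of best response and date of progression will be determined by modifying RECIST 1.1 criteria to assess tumors in individual organ systems independently".

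**Permission to operate.** On patients whose non-renal lesions are resected without having met progression, section 6.1 says they "may resume treatment with PT2385 once the surgical incisions have adequately healed", subject to the investigator's view of likely benefit. Section 6.4 requires interruption for non-renal surgery and then says: "Study drug may be restarted when the surgical incision has adequately healed", provided that ccRCC has not progressed and the interruption has not exceeded 8 weeks. Imaging is every 12 weeks for as long as the patient continues in the study (section 6.1).

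**Radiotherapy.** Section 8.2: "Patients may receive limited fraction palliative radiotherapy after 12 weeks to control local tumor-related symptoms". The field may not include a target lesion; irradiating one counts as progression and ends treatment.

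**Existing censoring rule.** Section 13.3.4 right-censors ccRCC PFS for, among other things, "non protocol systemic anticancer treatment started before documentation of disease progression or death" and surgery thought to affect response. The ccRCC DOR paragraph adopts the same rule. The organ-level paragraph does not.

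**The concern.** The organ-level endpoints are meant to show what PT2385 does to pancreatic, adrenal, CNS and other VHL lesions. Section 4.2 describes monitoring and surgery as current practice, and section 10.1.2.1 expects some patients to have tumors excised during the study. The plan recognises that surgery can contaminate ccRCC PFS and DOR, yet has no matching rule for the lesions whose resection it expressly permits.

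Without one, an operation can be credited to the drug. Section 4.2 says systemic treatment is wanted to delay or avoid surgery, so this would count the opposite of the aim as a success. Response is also assessed by both the investigators and the IRC, and with no written rule the two could classify the same resection differently.

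**Working it through.** There is no stated figure to reproduce: the plan gives no size, rate or precision for any non-ccRCC endpoint. The check is a reading of the rules followed by an illustration.

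**Step 1: does any rule stop a post-surgery scan from counting?**

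| Place | What it covers | Reaches organ-level response after resection? |
|---|---|---|
| 13.3.4, PFS censoring | ccRCC PFS | No |
| 13.3.4, DOR paragraph | ccRCC DOR, by reference to the PFS rule | No |
| 13.3.4, confirmation rule | ccRCC CR and PR | No; and a removed lesion is also absent on the next scan |
| 13.3.4, organ-level paragraph | Non-ccRCC ORR, best response, PFS, DOR, TTR | No cut-off stated |
| 13.3.1, missing data | Refers back to the endpoint definitions | No rule there |
| Appendix 3 | RECIST 1.1 summary tables | Nothing on a resected lesion |
| Appendix 4 | Assessment by lesion type | Nothing on a resected lesion |
| 6.1 and 6.4, withdrawal | Non-ccRCC lesions that progress | No; resection without progression is the permitted route |

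**Step 2: trace a patient.** Suppose a sole pancreatic target lesion is resected between the Week 13 and Week 25 scans, and drug is resumed. The lesion is absent at Week 25 and again at Week 37. Read literally, Appendix 3 can give target CR at both, hence an organ-level CR, or PR if non-target lesions remain. Dating by the first assessment, as section 13.3.4 does for confirmed responses, puts the response at Week 25. TTR is then the time to a scan that records surgery, DOR runs until regrowth or a new lesion, and organ-level PFS continues although the lesion at risk has gone.

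**Step 3: size per patient.** The patient stays in the denominator n, so each misclassification adds 1/n. Subgroup sizes are assumed:

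- n = 10: 1/10 = 10 percentage points
- n = 15: 1/15 = 6.7 percentage points
- n = 25: 1/25 = 4 percentage points

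**Step 4: size by frequency.** Let p be the true organ-level ORR and s the share of the remaining patients whose lesion is removed and scored CR or PR. Then apparent ORR = p + (1 − p) × s. Both inputs are assumptions.

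| True ORR p | s = 5% | s = 10% | s = 20% |
|---|---|---|---|
| 0% | 5% | 10% | 20% |
| 10% | 14.5% | 19% | 28% |
| 20% | 24% | 28% | 36% |

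For example, 0.10 + 0.90 × 0.10 = 0.19. With an assumed 20 patients and two true responders, 2/20 = 10% (exact 95% CI 1.2% to 31.7%). If two resections are also scored as responses, this becomes 4/20 = 20% (5.7% to 43.7%). With a cut-off at local therapy the surgical contribution is zero.

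**The case against.** **The plan is silent; it does not direct this scoring.** True. Appendix 3 has a not-evaluable outcome that a reader could apply to a removed lesion, the IRC also determines response, and removing one of several lesions need not produce a response. So the supportable wording is that a resected lesion could be scored as PR or CR. The gap still stands, because nothing requires the not-evaluable reading.

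**Few patients may be exposed.** Patients with an immediate need for surgery are excluded at entry, progressing non-ccRCC lesions lead to withdrawal, and resumption is conditional. This limits the size by an unknown amount; it does not supply a rule.

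**Detail is left to a later SAP.** Section 13 does foresee a formal SAP before final database lock. That makes the change easy, but section 13.3.4 already sets out censoring for ccRCC and omits it here.

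**A reader might infer the same hole in the primary ccRCC ORR**, since section 6.1 says of ccRCC response: "A response will be defined as either a PR or CR occurring at any time after initiation of treatment". The documents do not support that. Resumption after surgery is provided for non-renal lesions only; any other interruption beyond 3 weeks means withdrawal; section 8.2 prohibits chemotherapy and investigational anti-neoplastic agents; and Appendix 1 schedules no tumor assessment after treatment ends. No comparable route to a falsely credited ccRCC response is shown.

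**A reader might also give radiotherapy equal weight.** The route is narrow. The field may not cover a target lesion, and where target disease exists Appendix 3 requires a target-lesion CR or PR for an overall PR. What remains open is whether the term target lesion in section 8.2 includes those followed for the organ-level assessments.

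**Conclusion.** The point holds for resection and the organ-level secondary endpoints. Surgery on non-progressing non-renal lesions with later resumption of drug is expressly allowed, and no rule separates post-surgery scans from drug effect. The possible error favours PT2385 in ORR and best response, and can prolong organ-level PFS and DOR. The error in ORR is in the numerator; these patients do not leave the denominator.

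The size cannot be fixed from the documents. Under assumed subgroups of 10 to 25 patients it is 10 down to 4 percentage points of organ-level ORR per misclassified patient. It would be wrong to set such figures against the 15% null rate: that belongs to the ccRCC hypothesis, and the organ-level endpoints have no threshold. Nor do the documents show that the secondary objective is unanswerable. These are descriptive summaries, so this is a change that should be made, not one on which the trial's main conclusion depends.

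**What to change.** In section 13.3.4, and in the SAP that follows from it, state for each organ system:

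- Best response, TTR and DOR use only assessments before the first local therapy (resection, ablation or radiotherapy) to a lesion in that organ, or before the first non-protocol systemic anticancer therapy, whichever is earlier.
- A PR or CR first seen after that point is not a response, and the patient stays in the denominator.
- Organ-level PFS and DOR are censored at the last assessment before that therapy. Because surgery may be informative, a supplementary PFS analysis counts the local therapy as an event.
- The number of patients with local therapy is reported for each organ.

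Make sure that the CRF captures the date and organ of each local therapy. The documents specify surgical history at screening and in long-term follow-up, but do not expressly list on-treatment procedures by date and organ.

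**Cost.** Analysis wording and, if needed, a CRF field; no change to treatment rules or sample size. Organ-level ORR may be lower. With 12-weekly scans, a true PR seen before surgery but not yet confirmed would count as a non-response; show these patients in a sensitivity analysis. Later scans of untreated lesions in the same organ are also lost to the main summary.

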6.5. Criteria for Study Termination

If more than 2 of the first 6 patients enrolled in the first stage of the study experience treatment-limiting toxicity within the first 4 weeks of their treatment, the protocol will be modified or the study will be stopped. If after the first 25 patients have been enrolled in the study, 2 or fewer patients have had a confirmed ccRCC tumor response of PR or better, further enrollment will be temporarily suspended for up to a year or until at least 3 confirmed responses are seen. If 3 confirmed responses have not been observed within1 year after enrollment of the 25th patient, no further patients will be enrolled and the study will be stopped.

A Data Monitoring Committee (DMC) will perform the safety review for the first 6 patients and the futility analysis for Stage 1 of the study. The DMC will consist of the Principal Investigator(s) participating in this study, the Medical Monitor, and representatives from Peloton. The DMC will meet shortly after the sixth patient has been observed for 28 days after the administration of their initial PT2385 dose. The DMC will review safety and any treatment-limiting toxicities to confirm whether the study should continue to enroll or if modifications to the protocol are needed. The DMC will review the response data from the first 25 patients to determine if at least 3 patients have a confirmed PR or better in ccRCC tumors and that the threshold for opening Stage 2 has been met. Treatment-limiting toxicities will be assessed according to Section 6.4.

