13.1. Determination of Sample Size

This study will be conducted with a 2-stage design (Green and Dahlberg, 1992) which allows for an early assessment of futility. If after the first 25 patients have been enrolled to the study, 2 or fewer patients have had a confirmed response, further enrollment will be temporarily suspended for up to a year or until at least 3 responses are seen; if 3 responses are not seen within 1 year after enrollment of the 25th patient, no further patients will be enrolled and the study will be discontinued. In addition, if more than 2 of the first 6 patients enrolled experience treatment-limiting toxicity during the first 4 weeks of their treatment, the protocol will be modified or the study will be stopped. If 3 or more of the 25 patients respond, enrollment will proceed to the second stage of the design.

A total of 25 patients will be enrolled into the second stage of the study for a total required enrollment of 50 patients. If at least 13 of the 50 patients (25 + 25) respond (CR or PR), then the hypothesis that PT2385 is ineffective will be rejected.

The required sample size for this 2-stage design is based on the following design parameters: The null hypothesis is that PT2385 is ineffective, defined as an ORR (best confirmed response of PR or CR) of 15% (P_0 =0.15). The alternative hypothesis is that PT2385 is effective, defined as an ORR of 30% (P_1 =0.3). The probability of falsely concluding that the agent is effective when it is truly ineffective is 0.05 (alpha) and the probability of falsely concluding that the agent is ineffective when it is truly effective is 0.2 (beta).

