The determination of response and progression will be made by the local investigators. The investigator assessments will be used for decisions regarding treatment for individual patients and by the DMC for approval to open Stage 2 of the study. The response outcomes will also be reviewed and determined by an Independent Review Committee (IRC). For the primary analysis of ORR, the determination of response will be based on independent radiologic assessment conducted by the IRC. Both the investigators' and the IRC's assessments will be used for the summaries and analyses of efficacy.

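### The 1-year limit on the Stage 2 gate can close the study while a response already seen is waiting for its confirming scan

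*Combined protocol and SAP*

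**What the plan says.** **The gate.** Section 6.1: "Twenty-five patients will be enrolled during the first stage". Under Section 13.1 and the synopsis, accrual is suspended if "2 or fewer patients have had a confirmed response", for up to a year. The study is discontinued "if 3 responses are not seen within 1 year after enrollment of the 25th patient". Section 6.5 puts the limit explicitly on confirmed responses: "If 3 confirmed responses have not been observed within1 year after enrollment of the 25th patient", enrolment ends and the study stops.

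**The endpoint.** Section 6.1 sets no time limit: "A response will be defined as either a PR or CR occurring at any time after initiation of treatment", with confirmation required afterwards. Section 13.4.1 places the final analysis after all patients have completed the study.

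**Scans and confirmation.** Section 10.1.1 and Appendix 1 schedule imaging in the 7 days before the Week 13 visit and every 12 weeks after that. Section 13.3.4 asks for confirmation by a second assessment. If that assessment is not available, the next scheduled one serves. Appendix 1 lists no separate confirmation scan.

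**The reader.** Under Section 13.3.4, investigator assessments are used "by the DMC for approval to open Stage 2 of the study". For the final result, "For the primary analysis of ORR, the determination of response will be based on independent radiologic assessment conducted by the IRC".

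**The concern.** Section 13.1 treats the gate (at least 3 of 25) and the final rule (at least 13 of 50) as counts of one endpoint with one response probability. They differ in time window: the gate counts only what is confirmed by a calendar date, while the final count takes everything confirmed later as well. With 12-week scan spacing, a response can be on record at the cap and still not count. No provision covers that case. At stake is the end of a study of an effective drug for want of one scan that is already on the schedule.

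The two counts also differ in reader, which affects how often the gate would stop an ineffective drug.

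**Working it through.** **1. The plan's own rule.** Inputs from Section 13.1: 25 + 25 patients, stop at 2 or fewer of 25, reject at 13 or more of 50, null ORR 0.15, alternative 0.30, stated alpha 0.05 and beta 0.2.

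P(stop) = P(X ≤ 2), X ~ Bin(25, p).
- p = 0.15: 0.254
- p = 0.30: 0.009

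P(reject) = Σ over x ≥ 3 of P(X = x) × P(Y ≥ 13 − x), Y ~ Bin(25, p).
- p = 0.15: 0.030
- p = 0.30: 0.776

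The exact values differ from the stated alpha of 0.05 and power of 0.80. That is a separate matter; 77.6% is the reference below. The protocol states no stopping probabilities; 25.4% and 0.9% are what its rule implies.

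**2. The calendar.** The Week 13 visit falls 12 weeks after the start of treatment, so scans fall at about 12, 24, 36, 48 and 60 weeks. Taking enrolment as the start of treatment, the cap for the 25th patient is at 52 weeks.
- First seen at 36 weeks, confirmed at 48: counts.
- First seen at 48 weeks, confirmed at 60: 60 − 52 = 8 weeks too late.

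Earlier patients have longer follow-up, but the gap is not confined to the 25th. Any patient's last scheduled scan before the cap is followed by one after it, so a response first seen at that last scan cannot be confirmed on schedule in time.

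**3. Effect at a true ORR of 30%.** Let s be the share of Stage 1 responses confirmed by the cap (an assumption; the documents give no time-to-response distribution).

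P(stop) = P(X ≤ 2), X ~ Bin(25, 0.30 × s).

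Power = Σ over x of P(Bin(25, 0.30) = x) × P(Bin(x, s) ≥ 3) × P(Bin(25, 0.30) ≥ 13 − x).

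| s | 0.30 × s | P(stop) | Power |
|---|---|---|---|
| 1.00 | 0.300 | 0.9% | 77.6% |
| 0.80 | 0.240 | 4.1% | 76.5% |
| 0.67 | 0.201 | 9.6% | 73.6% |
| 0.50 | 0.150 | 25.4% | 62.9% |

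**4. If only late enrollees are affected.** Losing just the 25th patient's response at the gate gives P(stop) 1.2% and power 77.6%. If the last 5 patients each lose half their responses (assumed), the figures are 1.9% and 77.4%.

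**5. Type I error.** A futility gate can only remove rejections. With no gate, 13 or more of 50 at p = 0.15 has probability 0.0301, so alpha cannot exceed that.

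**6. What a hold rule recovers.** Simulation at ORR 30%, with these assumptions: exponential time to response with median 24 to 36 weeks, even Stage 1 accrual over 26 to 52 weeks, scans every 12 weeks, and every response confirmed at the next scan. Holding the decision for pending confirmations cuts false stopping from about 4–15% to about 3–9% and recovers about 0.5 to 4 points of power.

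**7. The reader.** If the IRC rate is 15% but the investigator rate is higher (assumed), expected N = 25 + 25 × (1 − P(stop)):

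| Investigator rate | P(stop) | Expected N |
|---|---|---|
| 15% | 25.4% | 43.7 |
| 20% | 9.8% | 47.5 |
| 25% | 3.2% | 49.2 |

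The two effects pull in opposite directions. If 70% of IRC responders and 5% of IRC non-responders count at the gate (assumed), P(stop) under the null is 26.5%, close to 25.4%, and power is 76.3%.

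**The case against.** The plan anticipates slow responses: the suspension of up to a year exists for that purpose, and 3 of 25 (12%) is a lenient bar against an alternative of 30%. Section 13.3.4 makes the next scheduled scan a fallback, so an earlier confirming assessment is possible. The year runs from the 25th enrolment, so the other 24 patients have longer, and applying one share to all 25 is a rough model. The larger losses need a third to a half of all Stage 1 responses to be unconfirmed at the cap, which nothing in the documents supports. All of this stands and limits the size. It does not fill the gap: no earlier confirming scan is scheduled, and no text says what happens to a response pending at 1 year.

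Section 13.1 and the synopsis speak only of responses seen when they state the limit. That could be read as counting unconfirmed ones, but Section 6.5 says confirmed.

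A reader might go further and infer that the reader mismatch defeats the gate, particularly as "The DMC will consist of the Principal Investigator(s) participating in this study", with the Medical Monitor and sponsor representatives. The documents do not support that. They give no discordance rate, so neither its direction nor its size is known. Investigator reads for this operational decision are prespecified and kept apart from the IRC-based primary analysis. Nor is the gate the only early stop: Section 6.5 also provides for modifying or stopping the study on treatment-limiting toxicity in the first 6 patients.

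**Conclusion.** The concern holds for the time limit. As written, the study can be closed with a qualifying PR or CR on record and its confirming scan still to come. The implied 0.9% false-stopping probability at ORR 30% requires every Stage 1 response to be confirmed by the cap. With 80% or 67% confirmed it is 4.1% or 9.6%, and power falls by 1.1 or 4.0 points from 77.6%. These shares are assumptions, and if only the last few enrollees are affected the loss is a fraction of a point.

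It would be wrong to conclude that the false-positive rate rises (it is at most 0.030) or that power will drop to 62.9%, which needs half of all responses to be late. On the reader, the stopping probability under the IRC null is 25.4% only if investigator and IRC rates agree. That is an unreported dependence, not a contradiction.

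**What to change.** Add to Sections 6.5 and 13.1 and the synopsis: if fewer than 3 responses are confirmed 1 year after the 25th enrolment, but unconfirmed PR or CR already seen could bring the count to 3, the futility decision is held until those patients' next scheduled scan. Use the term confirmed in all three places when stating the limit.

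The cost is at most about 12 weeks' delay, in borderline cases only, with no additional scan or reader. The rule does not recover responses first seen after the cap, so it restores part of the lost power, not all of it.

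Optionally, report in Section 13.1 the stopping probability and power over a stated range of investigator–IRC discordance. Moving the gate to IRC reads would align the two counts but requires earlier central reading of 25 patients. That is a trade-off for the sponsor to weigh, not a required correction.
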